### **5. Anxiety and Depression Survey risks:**

The survey asks sensitive questions about mental health. To reduce discomfort while answering questions, you will answer questions in a private room. Participants are free to not answer any questions. Confidentiality risks are minimal and unlikely to occur. Your child's confidentiality will be protected to the greatest extent possible.

If subject reports any concerning symptoms, we will provide referrals and information on how to get help.

## **Protection of Human Subjects**

All studies will be performed under the direct supervision of either the PI or co-investigators. Phlebotomy discomfort will be minimized by personnel skilled in venipuncture of children and obese patients.

Gastrointestinal side effects with metformin will be minimized by slow incremental dose increases over the course of two weeks. The PI has extensive experience with metformin and has used it in a clinical trial published in 2008. In terms of spironolactone treatment, potential subjects will be interviewed separately from their parents with our Adolescent Medicine co-investigators regarding their sexual activity. A patient who is sexually active will be excluded from participating in the study. Furthermore, subjects will be counseled on the potential teratogenic effects of spironolactone and the requirements of monthly pregnancy tests. Should a subject not comply with monthly pregnancy testing, then she will be discontinued from the study. Should a patient decide to become sexually active during the study, she will also be

discontinued from the study. Should a subject's pregnancy test turn positive then she will be discontinued of both intervention drugs. At that point the principal investigator will meet with the IRB to discuss recommendations in terms of following pregnancy outcome.

Prior to commencing spironolactone/metformin the PI will assess kidney functions and examine electrolytes with attention to potassium levels. Any abnormalities in one or both of these areas will prohibit entry into the trial. Subjects will be given the number of the principal investigator and the RA. They will also be given an emergency number that is available at all times through the section of Pediatric Endocrinology. All on call staff will be aware of the study.

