Spironolactone has been used for decades as a potassium sparing diuretic and was found to have anti-androgenic effect in the 1970's . Its anti-androgenic effect is carried out through a dual mechanism of androgen receptor blockade, and via spironolactone's inhibition of 5-alpha reductase, thus reducing the conversion of testosterone to its biologically more potent metabolite, di-hydrotestosterone. The concern with studying spironolactone in adolescent girls has always been the potential effect of the drug to under-virilize a male embryo through transplacental exposure of the drug, should an unplanned pregnancy occur. However, unlike the widely prescribed OC, spironolactone does not pose a serious health risk (i.e thrombo-embolic events) to the patient herself  and therefore is the safer drug for the subject, especially if she is overweight and has a family history of thrombo-embolism events. Furthermore, a recent study in adolescent girls with hirsutism, demonstrated that a carefully designed study does not need to preclude adolescents from receiving anti-androgen therapy . In this study, adolescent girls with hirsutism were treated with the potent anti-androgen finasteride for 6 months and were not on oral contraceptive pills. In our proposed study, risk will be reduced by precluding sexually active teens from partaking in the study. Furthermore, all participants, even if not sexually active will be required to take a monthly pregnancy test for the duration of the study. This would likely safeguard against any inadvertent exposure of a male conceptus to spironolactone, as study drug would be discontinued immediately in the event of a positive pregnancy test. Lastly there has been a case report on a young woman treated with spironolactone (200-400mg daily) throughout each of her pregnancies due to Bartter Syndrome. In the case description she delivered two normal male infants and one normal female. At the time of the report one of the males had entered puberty at a physiologic time. While the teratogenic concern remains based on some, but not all animal studies carefully selected subjects and stringent protocol adherence should allow this very beneficial drug to be examined in adolescents with PCOS.

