### **4. Spironolactone**

In general this drug is very well tolerated and poses no health risk in low dose. Given that spironolactone is a potassium-sparing diuretic it may elevate potassium levels in those with underlying kidney disease or excessive potassium intake. In the absence of contraindications like renal failure and in a presence of healthy well-balanced diet, spironolactone is unlikely to increase potassium levels outside the normal range. Should a subject not maintain a normal hydration status she may feel dizzy/lightheaded. This can be avoided by normal fluid intake. The main concern is the potential of this drug to under-virilize a male conceptus. Therefore, sexually active teenagers are excluded from the study. Nevertheless, every subject will be monitored with monthly urine pregnancy tests to assure that the study drug is not continued beyond the first two weeks post conception should an unexpected pregnancy occur. Study drugs will be immediately discontinued should a positive pregnancy test have occurred.

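### Followed as written, removal for a missed pregnancy test or for sexual activity also ends pregnancy surveillance, so an exposure that has already occurred could go undetected

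*Combined protocol and SAP*

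**What the plan says.** Three sections of the combined protocol and SAP bear on this.

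- **Risks and Inconveniences, 4. Spironolactone.** The principal hazard is named: "The main concern is the potential of this drug to under-virilize a male conceptus". The section relies on "monthly urine pregnancy tests to assure that the study drug is not continued beyond the first two weeks post conception".
- **B) Background and Significance.** The testing period is set here: "all participants, even if not sexually active will be required to take a monthly pregnancy test for the duration of the study".
- **Protection of Human Subjects** (the section after the risk descriptions). The first removal rule reads "Should a subject not comply with monthly pregnancy testing, then she will be discontinued from the study". The next sentence begins "Should a patient decide to become sexually active during the study, she will also be" and ends with the same removal from the study. A positive test has a different consequence: the girl stops both study drugs, and nothing is said about her leaving the study. Only then does the plan turn to the outcome of the pregnancy, where "the principal investigator will meet with the IRB to discuss recommendations in terms of following pregnancy outcome".

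The visible text describes no pregnancy test at or after removal, and no later contact to establish whether a removed girl is pregnant. It does not define what removal from the study stops and what it leaves running.

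**The concern.** Testing is attached to being in the study, and the two removal rules take a girl out of the study. Read together, they end testing for two groups in whom the question is still open. A girl who missed her test has an unknown status. A girl who has become sexually active has a higher chance of conception than those who remain, because all of them are required not to be sexually active.

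The only route to outcome follow-up is a positive test. A girl removed without one cannot reach the discussion with the IRB, even if she conceived while taking spironolactone, and she would not learn of the exposure through the study. The plan also counts a birth defect among its grade 3 events (Plan for Grading Adverse Events). Such an event would usually become visible only after a 6-month intervention had ended, so the plan lists an event that it has no written way to observe in these girls. The Data and Safety Monitoring Plan justifies the moderate-risk classification partly by surveillance good enough to find adverse events quickly. For the main named hazard, that surveillance stops when a removal rule is triggered.

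**Working it through.** **The plan's own figure.** The plan gives no number on this point. Its one computed design figure is 93% power for the paired t-test (difference 8.0 − 4.7 = 3.3, standard deviation of change 4.0, n = 20). An exact noncentral t calculation gives 93.8%, so it reproduces, but it has no bearing here.

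**The rules side by side.**

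| Trigger | Stated consequence | Testing afterwards | Outcome follow-up |
|---|---|---|---|
| Missed monthly test | Leaves the study | None written | None written |
| Becomes sexually active | Leaves the study | None written | None written |
| Positive test | Both drugs stopped | Status already known | Raised with the IRB |

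The only trigger that leads to follow-up is the one where pregnancy has already been found.

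**How much time could be uncovered.** Inputs:

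- Test interval: monthly in the plan, taken as 30 days.
- Detection lag L, from conception to the first day a urine test is positive: not given in the documents. It is assumed here and ranged from 8 to 21 days.

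Suppose the last negative test was u days before removal. It could not see conceptions in the L days before it, and no test covers the u days after it. The uncovered window is therefore u + L days. Its maximum, with removal on the day the next test falls due, is 30 + L.

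Now suppose conceptions are spread evenly over the 30 days before removal, and u is equally likely to be anything from 0 to 30. The average share missed is the mean of min(30, u + L) divided by 30, which equals 1 − (30 − L)² / (2 × 30²). For comparison, a single test on the removal day would miss L / 30.

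| L (days) | Maximum window, 30 + L (days) | Share missed, no test at removal | Share missed, one test on removal day |
|---|---|---|---|
| 8 | 38 | 1 − 484/1800 = 73.1% | 26.7% |
| 10 | 40 | 1 − 400/1800 = 77.8% | 33.3% |
| 14 | 44 | 1 − 256/1800 = 85.8% | 46.7% |
| 21 | 51 | 1 − 81/1800 = 95.5% | 70.0% |

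A girl removed for a missed test sits at the maximum, because her last test was a full interval ago. For a girl removed for sexual activity, the window cannot begin before the activity did. If that was s days before removal, the window is the smaller of s and u + L. The shares in the table would then not apply to her unless activity spanned the whole 30 days.

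The last column is not a proposed schedule. It shows only that any positive lag leaves some recent conceptions unseen by a test on the day of leaving.

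**The case against.** The strongest reply is that the text never says surveillance stops. Removal from the study is undefined. Participants hold contact numbers for the investigator and the research assistant and an emergency number, and they are patients of the PCOS program. The flow chart that is said to show the complete design is not in the available text, and consent pages are not available either, so a test or a consent to outcome follow-up could be written there. The investigational pharmacy distributes both drugs, so removal presumably also ends supply and limits exposure. This stands as a caveat. It does not supply a written provision, and being able to call the team is not planned observation. It does mean that the gap concerns exposure that has already happened, not continued dosing, although the text does not state that removal stops the drug.

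Several stronger readings are tempting and are not supported:

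- **A 14-day detection lag.** A reader might take one from the statement that "the study drug is not continued beyond the first two weeks post conception should an unexpected pregnancy occur". That statement is a ceiling on exposure, not a property of the test, so no single lag can be credited to the plan.
- **The same failure in girls who complete treatment.** A girl who conceives in her last two weeks on drug and then finishes has at most two weeks of exposure after conception, which is within that ceiling. The point is confined to removed girls.
- **A missed test as a sign of higher risk.** It makes status unknown and shows nothing more.
- **A false claim that no pregnancy was exposed.** The documents plan no such conclusion and have no rule that counts removed girls as event-free. The trial is an uncontrolled pilot in 20 girls with an insulin sensitivity index as its primary outcome.

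**Conclusion.** The point holds as a gap in the written rules. On the visible text, pregnancy surveillance ends at removal for girls whose status is unknown or whose risk has risen, and the one route to outcome follow-up is closed to them.

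With an assumed detection lag of 8 to 21 days and tests 30 days apart, up to 38 to 51 days before removal could be uncovered by an informative test, and less where sexual activity began recently. The lag and the 30-day interval are assumptions. The existence of a gap needs only that the lag is greater than zero and that nothing in the missing flow chart or consent pages fills it. The number of girls affected is unknown and cannot exceed 20, but in a study of that size one unobserved exposure would matter to the safety summary. The primary analysis of insulin sensitivity is not touched by this point.

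**What to change.** Reword the two removal sentences under Protection of Human Subjects so that they end study treatment but keep the girl in pregnancy and adverse-event follow-up.

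Then reconcile that section with B) Background and Significance and with 4. Spironolactone on two matters: when pregnancy surveillance ends, and how the outcome of a pregnancy exposed to study drug is followed. If the flow chart or the consent form already covers this, a cross-reference in the text would be enough. The timing and number of any tests, and the clinical rule itself, are for the sponsor to set.

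The cost is amendment and consent wording, and a short extra follow-up contact for at most 20 girls.

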### **Data and Safety Monitoring Plan**

The proposed study poses moderate risk to the subjects. However, it offers the prospect of direct benefits to the subjects. The definition of moderate risk is as follows: Risks are recognized as being greater than minimal, but not high, and there is adequate surveillance and protections to discover adverse events promptly and to keep their effects minimal.

### **Attribution of Adverse Events**

- **Definite:** Adverse event(s) will clearly be related to investigational agent(s) or other intervention.
- **Probable:** Adverse event(s) will likely be related to investigational agent(s).
- **Possible:** Adverse event(s) may be related to investigational agent(s).
- **Unlikely:** Adverse event(s) will doubtfully be related to investigational agent(s).
- **Unrelated:** Adverse event(s) will clearly not be related to the investigational agents(s).

### **Plan for Grading Adverse Events**

- 0 No adverse event or within normal limits
- 1 Mild adverse event
- 2 Moderate adverse event
- 3 Severe adverse event resulting in hospitalization or prolongation of existing hospitalization, a persistent or significant disability/incapacity, or a congenital anomaly/birth defect.
- 4 Life-threatening or disabling adverse event
- 5 Fatal adverse event

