### **3. Metformin**

The main side effect of metformin is gastrointestinal discomfort such as flatulence, queasiness, and loose bowel movements. Metformin therapy can cause malabsorption of vitamin B12 in the distal ileum after long-term use for several years. Therefore, vitamin B12 levels will be monitored in the study. Subjects will be recommended to stay on a well-balanced diet. Lactic acidosis is a rare but potentially fatal metabolic consequence of metformin treatment. However nearly all reports of lactic acidosis are related to treatment in a patient in which metformin therapy was contraindicated due to renal and liver dysfunction. In the absence of contraindications lactic acidosis is not of concern in otherwise healthy people.

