### **Plan for Reporting and Reviewing Serious Adverse Events**

Serious *unanticipated* adverse events will be reported immediately to the IRB. Serious *anticipated* adverse events where magnitude or frequency exceeds expectations will be reported to the IRB immediately.

The principal investigator will evaluate the adverse event and determine whether the adverse event affects the Risk/Benefit ratio of the study and whether modifications to the protocol (at Risks to Subjects, or in Procedures) or consent form (at Risks and Inconveniences) are required.

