### **Plan for Reviewing and Reporting Non-Serious Unanticipated and Anticipated Adverse Events.**

The principal investigator will conduct a review of all adverse events at the half-way point through the study. The principal investigator will evaluate the frequency and severity of the adverse events and determine if modifications to the protocol or consent form are required.

A summary of the adverse events will be reported to the IRB periodically or, at minimum, when re-approval of the protocol is sought. The summary will include number of subjects enrolled and a summary of graded adverse events to date.

Attribution	Grade 1	Grade 2	Grade 3	Grade 4	Grade 5
-------------	---------	---------	---------	---------	---------

	UNA TP	ATP	UNA TP	ANT	UNA TP	ANT	UNA TP	ANT	UNA TP	ANT
Unrelated										
Unlikely										
Possible										
Probable										
Definite										
Totals										
Total Subjects Enrolled to Date										

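### Do Grades 3 and 4 of the adverse-event scale leave some severe events with no grade, or with two?

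*Combined protocol and SAP*

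**What the plan says.** The Plan for Grading Adverse Events sets a scale from 0 to 5. Grades 1 and 2 are the bare words mild and moderate, with no criteria. Grade 3 is "Severe adverse event resulting in hospitalization or prolongation of existing hospitalization, a persistent or significant disability/incapacity, or a congenital anomaly/birth defect". Grade 4 is "Life-threatening or disabling adverse event", and Grade 5 is a fatal event. The text available gives no tie-break and cites no external grading scale.

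The grades are used in the section on non-serious unanticipated and anticipated adverse events. There the principal investigator reviews all adverse events half-way through the study and is to "evaluate the frequency and severity of the adverse events" in deciding whether the protocol or consent form needs modifying. On what goes to the IRB, the section says: "The summary will include number of subjects enrolled and a summary of graded adverse events to date". The table shell that follows has columns for Grades 1 to 5 and rows for attribution.

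The faster route is set out under Plan for Reporting and Reviewing Serious Adverse Events, where serious unanticipated "adverse events will be reported immediately to the IRB". Serious anticipated events go the same way if they are larger or more frequent than expected. Data Monitoring and Safety Reviews adds a review whenever a serious event occurs.

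**The concern.** A grading scale should give each event exactly one grade, and read literally this one may fail in two ways.

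- **Overlap.** Lasting or significant disability is one of the Grade 3 outcomes, while Grade 4 covers any disabling event. The same event satisfies both lines.
- **Gap.** Grades 1 and 2 are severity words alone, but Grade 3 attaches outcomes to its severity word. If those outcomes are required, a severe event managed at home is too severe for Grade 2, lacks a Grade 3 outcome, and does not reach Grade 4 or 5.

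The gap seems possible here because subjects are generally healthy outpatients. The risk section names effects that need not lead to admission: "The main side effect of metformin is gastrointestinal discomfort such as flatulence, queasiness, and loose bowel movements" and, for spironolactone, "it may elevate potassium levels in those with underlying kidney disease or excessive potassium intake", with the warning that a poorly hydrated subject "she may feel dizzy/lightheaded".

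At stake is the consistency of the graded safety summary. A severe outpatient event might be recorded as Grade 2, recorded as Grade 3, or left out of the table, and a disabling event might be Grade 3 on one occasion and Grade 4 on another. The principal investigator is the only named safety reviewer, so the summary is a main route by which the IRB sees non-serious events.

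**Working it through.** The plan gives no figure on this point and no arithmetic applies. The check sets the grade definitions against one another and then asks what depends on the grade.

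**1. Can an event have two grades?** Yes. A severe event that causes persistent or significant disability meets Grade 3 through its listed outcome and Grade 4 through the word disabling. Nothing in the safety sections chooses between them. The scale is ordered, however, and taking the higher of two applicable grades is the natural choice.

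**2. Can an event have no grade?** That depends on how Grade 3 is read.

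| Reading of Grade 3 | Severe event, no listed outcome, not life-threatening, disabling or fatal |
|---|---|
| Severity is judged separately, and a listed outcome is also required | Fits no grade |
| The listed outcomes are what makes an event severe in this protocol | Cannot occur; a lesser event is Grade 1 or 2 |

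The first reading follows the grammar more closely. It needs, though, a meaning of severe that stands apart from the outcomes, and the protocol supplies none: mild, moderate and severe have no other definition. The second reading is therefore also open, and the gap is conditional.

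**3. Do the described drug effects make the gap likely?** The documents do not show it.

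- The metformin section speaks of gastrointestinal discomfort, and the two-week dose build-up is meant to limit it.
- Vitamin B12 malabsorption is described as following several years of use, whereas this intervention lasts 6 months.
- A potassium rise beyond the normal range is called unlikely without contraindications, and the exclusion criteria remove subjects with raised potassium or creatinine.
- Dizziness is tied to poor hydration and described as avoidable.

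Any of these could in principle be judged severe in a subject who is not admitted, but that is a clinical supposition and the documents give no rate for it.

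**4. What depends on the grade?**

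| Plan element | Trigger or input | Uses a grade cut-off? |
|---|---|---|
| Immediate report to the IRB | Serious, and unanticipated or beyond expectation | No |
| Unscheduled data and safety review | A serious event | No |
| Half-way review | All adverse events, by frequency and severity | No |
| Stopping or modifying the study | Judgement of the principal investigator or the IRB | No |
| Periodic IRB summary | Counts by grade and attribution | Grade sets the column only |
| Primary analysis | Paired comparison of WBISI before and after treatment | No |

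Only the summary table is sensitive to the grade, and only in where an event is placed.

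**5. Would rewriting Grade 3 help?** Defining it by severity alone would close the gap under the first reading. It would also remove the only concrete criteria in Grades 1 to 3, leaving three undefined adjectives in a row. Grading could become less consistent, which is the harm the change is meant to prevent.

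**The case for a change.** The best case for a change runs as follows. The Grade 3 wording states a condition and is not offered as an example, so placing a severe outpatient event in Grade 3 departs from the text, and Grade 2 is equally open to the grader. Taking the highest applicable grade settles the overlap but does nothing for an event that meets no grade. The table has no column for an ungraded event, so the IRB might not see it there. The available text also never says what makes an event serious, although that word drives immediate reporting. The repair would cost some wording and one yes/no field per event.

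Part of this stands. The overlap is literal. The gap exists on one of the two readings. It is also true that a highest-grade rule leaves that gap open.

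The rest carries less weight. An event that is hard to grade is still an adverse event and still falls within the half-way review of all events. A grader faced with it would choose an adjacent column, and no action in the plan changes with that choice. The missing definition of serious cannot be pressed far: the contents page lists an adverse-events item under Miscellaneous Considerations that does not appear in the text available, so its absence from the full plan is not established. The same caution applies to a missing tie-break. Finally, the low cost of the repair has to be set against the loss of the only criteria that now anchor Grades 1 to 3.

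**Conclusion.** The concern does not call for a change to the plan. What survives is a small wording overlap: a disabling event meets both Grade 3 and Grade 4. The claim that some severe events have no grade holds only if the Grade 3 outcomes are read as an added requirement, and the protocol equally allows them to be its meaning of severe.

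The effect is confined to the column an event takes in a descriptive table for 20 subjects. No event is lost to review, no reporting trigger or stopping decision turns on a grade, and the WBISI result and its power statement are unaffected. This is a detail that an investigator can fill sensibly when grading, and the obvious rewrite is a debatable trade with no clear gain.

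The conclusion rests on two assumptions: that the half-way review covers all adverse events, as written, and that no part of the plan outside the available text ties an action to a particular grade. If such a link existed, the overlap would matter more.
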